4.1.2 Pharmaceutical and Therapeutic Background

4.1.2.1 Pembrolizumab (MK-3475)

The importance of intact immune surveillance in controlling outgrowth of neoplastic transformation has been known for decades. Accumulating evidence shows a correlation between tumor-infiltrating lymphocytes (TILs) in cancer tissue and favorable prognosis in various malignancies. In particular, the presence of CD8+ T-cells and the ratio of CD8+ effector T-cells / FoxP3+ regulatory T-cells seems to correlate with improved prognosis and long-term survival in many solid tumors.

The PD-1 receptor-ligand interaction is a major pathway hijacked by tumors to suppress immune control. The normal function of PD-1, expressed on the cell surface of activated

T-cells under healthy conditions, is to down-modulate unwanted or excessive immune responses, including autoimmune reactions. PD-1 (encoded by the gene *Pdcd1*) is an Ig superfamily member related to CD28 and CTLA-4 which has been shown to negatively regulate antigen receptor signaling upon engagement of its ligands (PD-L1 and/or PD-L2). The structure of murine PD-1 has been resolved. PD-1 and family members are type I transmembrane glycoproteins containing an Ig Variable-type (V-type) domain responsible for ligand binding and a cytoplasmic tail which is responsible for the binding of signaling molecules. The cytoplasmic tail of PD-1 contains 2 tyrosine-based signaling motifs, an immunoreceptor tyrosine-based inhibition motif (ITIM) and an immunoreceptor tyrosine-based switch motif (ITSM). Following T-cell stimulation, PD-1 recruits the tyrosine phosphatases SHP-1 and SHP-2 to the ITSM motif within its cytoplasmic tail, leading to the dephosphorylation of effector molecules such as CD3 ζ , PKC θ and ZAP70 which are involved in the CD3 T-cell signaling cascade. The mechanism by which PD-1 down modulates T-cell responses is similar to, but distinct from that of CTLA-4 as both molecules regulate an overlapping set of signaling proteins. PD-1 was shown to be expressed on activated lymphocytes including peripheral CD4+ and CD8+ T-cells, B-cells, T regs and Natural Killer cells. Expression has also been shown during thymic development on CD4-CD8- (double negative) T-cells as well as subsets of macrophages and dendritic cells. The ligands for PD-1 (PD-L1 and PD-L2) are constitutively expressed or can be induced in a variety of cell types, including non-hematopoietic tissues as well as in various tumors. Both ligands are type I transmembrane receptors containing both IgV- and IgC-like domains in the extracellular region and contain short cytoplasmic regions with no known signaling motifs. Binding of either PD-1 ligand to PD-1 inhibits T-cell activation triggered through the T-cell receptor. PD-L1 is expressed at low levels on various non-hematopoietic tissues, most notably on vascular endothelium, whereas PD-L2 protein is only detectably expressed on antigen-presenting cells found in lymphoid tissue or chronic inflammatory environments. PD-L2 is thought to control immune T-cell activation in lymphoid organs, whereas PD-L1 serves to dampen unwarranted T-cell function in peripheral tissues. Although healthy organs express little (if any) PD-L1, a variety of cancers were demonstrated to express abundant levels of this T-cell inhibitor. PD-1 has been suggested to regulate tumor-specific T-cell expansion in subjects with melanoma (MEL). This suggests that the PD-1/PD-L1 pathway plays a critical role in tumor immune evasion and should be considered as an attractive target for therapeutic intervention.

Pembrolizumab is a potent and highly selective humanized monoclonal antibody (mAb) of the IgG4/kappa isotype designed to directly block the interaction between PD-1 and its ligands, PD-L1 and PD-L2. Keytruda™ (pembrolizumab) has recently been approved in the United States for the treatment of patients with unresectable or metastatic melanoma and disease progression following ipilimumab and, if BRAF V600 mutation positive, a BRAF inhibitor.

4.1.3 Preclinical and Clinical Trial Data

Refer to the Investigator's Brochure for Preclinical and Clinical data.

4.2 Rationale

4.2.1 Rationale for the Trial and Selected Subject Population

The Programmed death Ligand 1 (PD-L1) / programmed death receptor (PD-1) axis has been identified as an important regulator of the immune system across various solid tumors allowing cancer cells to escape immune response [16]. The normal function of PD-1, an Ig superfamily member related to CD 28 and CTLA-4, expressed on the cell surface of activated T- cells under healthy conditions, is to down modulate unwanted or excessive immune responses, including autoimmune reactions. The ligands for PD-1 (PD-L1 and PD-L2) are constitutively expressed or can be induced in a variety of non-hematopoietic tissues as well as in various tumors. Binding of either PD-1 ligand to PD-1 inhibits T cell activation triggered through the T- cell receptor.

Head and neck squamous cell carcinoma has a prominent immune escape in both HPV positive and negative settings [17, 18]. It has also been shown that in mouse model, blocking PD1/PDL1 interaction can result in tumor regression and survival extension.[19] In addition, it has been shown in pre-clinical models that following radiation, PD-L1 gets up-regulated in the tumor microenvironment and that anti-PD-L1 therapy can improve the efficacy of radiation through a cytotoxic T cell-dependent mechanism, supporting the hypothesis that a PD-L1 / PD-1 inhibitor can restore anti-tumor activity [32].

Pembrolizumab (MK-3475) is a potent and highly selective humanized monoclonal antibody designed to block the interaction between PD-1 and its ligands PD-L1 and PD-L2. It has been shown to have a potent and durable anti-tumor activity in multiple tumor types, including single agent activity in HNSCC [20]. Preliminary data reported in abstract form in 2014 revealed that 78% of RMSCC screened for an ongoing MK-3475 phase Ib study, expressed PD-L1. There have been observations of disease responses in this cohort of 60 patients, many of whom have been heavily pretreated with prior systemic agents[20]. However, combination of Pembrolizumab and chemo radiation has not been examined in humans, which remains important in better understanding of the therapeutic utility of this agent in the vast majority of locally advanced HNSCC.

Laryngeal squamous cell carcinoma is unique in the setting for which surgical options are less appealing due to long-term morbidities associated with a total laryngectomy (tracheostomy and loss of voice). Chemo-radiation alone may not be sufficient to avoid surgery and allow for a long-term survival of patients with a functional larynx. This disease is also unique in the setting that it is highly associated with smoking and genetic complexity, making it a favorable target for immune modulators. In addition, biologic correlative testing is feasible due to the accessibility of tumor tissue by biopsy and any specimens from patients undergoing laryngectomy for residual/ progressive or dysfunctioning larynx.

We propose a single arm phase II study to test the hypothesis that the addition of Pembrolizumab to chemoradiation enhances the local effects of standard therapy in laryngeal HNSCC, ultimately allowing for higher rates of functional organ preservation in this population, and leading to improved quality of life. In addition, we hypothesize that adding Pembrolizumab to chemo radiation may result in immune-mediated regression

of micrometastatic disease and lower rates of systemic relapse, similar to what has previously been described in distant untreated melanoma lesions [21] Therefore, we will examine not only laryngectomy-free survival and event-free survival endpoints [including death, persistent disease or progression, laryngectomy (partial or total), and feeding tube dependence], but also pattern of in and out of field tumor growth in these patients. Finally, we will examine exploratory correlative studies that will provide valuable insight into the effects of chemo radiation in combination with PD1 inhibitor on laryngeal carcinoma microenvironment, and the association of tumor response and overall clinical benefit with adaptive PD-L1 tumor expression, immune infiltration, cytokine expression profiles, and genomic signature of tumors. We hypothesize that chemo radiation affects expression of PD1/PD-L1 on tumor infiltrating immune cells detected by IHC and subsequently increases PD-L1 expression on the tumor cells, which will predict response to chemo radiation and PD-1 inhibitor.

We hypothesize by inhibiting PD1 ligands, PDL1 and PDL2, we will activate immune system and allow for better anti-tumor effect, finally resulting in improved laryngectomy-free survival with fewer side effects.

4.2.2 Rationale for Dose Selection/Regimen/Modification

An open-label Phase I trial (Protocol 001) is being conducted to evaluate the safety and clinical activity of single agent Pembrolizumab (MK-3475). The dose escalation portion of this trial evaluated three dose levels, 1 mg/kg, 3 mg/kg, and 10 mg/kg, administered every 2 weeks (Q2W) in subjects with advanced solid tumors. All three dose levels were well tolerated and no dose-limiting toxicities were observed. This first in human study of MK-3475 showed evidence of target engagement and objective evidence of tumor size reduction at all dose levels (1 mg/kg, 3 mg/kg and 10 mg/kg Q2W). No MTD has been identified to date. 10.0 mg/kg Q2W, the highest dose tested in PN001, will be the dose and schedule utilized in Cohorts A, B, C and D of this protocol to test for initial tumor activity. Recent data from other clinical studies within the MK-3475 program has shown that a lower dose of MK-3475 and a less frequent schedule may be sufficient for target engagement and clinical activity.

PK data analysis of MK-3475 administered Q2W and Q3W showed slow systemic clearance, limited volume of distribution, and a long half-life (refer to IB). Pharmacodynamic data (IL-2 release assay) suggested that peripheral target engagement is durable (>21 days). This early PK and pharmacodynamic data provides scientific rationale for testing a Q2W and Q3W dosing schedule.

A population pharmacokinetic analysis has been performed using serum concentration time data from 476 patients. Within the resulting population PK model, clearance and volume parameters of MK-3475 were found to be dependent on body weight. The relationship between clearance and body weight, with an allometric exponent of 0.59, is within the range observed for other antibodies and would support both body weight normalized dosing or a fixed dose across all body weights. MK-3475 has been found to have a wide therapeutic range based on the melanoma indication. The differences in

exposure for a 200 mg fixed dose regimen relative to a 2 mg/kg Q3W body weight based regimen are anticipated to remain well within the established exposure margins of 0.5 – 5.0 for MK-3475 in the melanoma indication. The exposure margins are based on the notion of similar efficacy and safety in melanoma at 10 mg/kg Q3W vs. the proposed dose regimen of 2 mg/kg Q3W (i.e. 5-fold higher dose and exposure). The population PK evaluation revealed that there was no significant impact of tumor burden on exposure. In addition, exposure was similar between the NSCLC and melanoma indications. Therefore, there are no anticipated changes in exposure between different indication settings.

The rationale for further exploration of 2 mg/kg and comparable doses of pembrolizumab in solid tumors is based on: 1) similar efficacy and safety of pembrolizumab when dosed at either 2 mg/kg or 10 mg/kg Q3W in melanoma patients, 2) the flat exposure-response relationships of pembrolizumab for both efficacy and safety in the dose ranges of 2 mg/kg Q3W to 10 mg/kg Q3W, 3) the lack of effect of tumor burden or indication on distribution behavior of pembrolizumab (as assessed by the population PK model) and 4) the assumption that the dynamics of pembrolizumab target engagement will not vary meaningfully with tumor type.

The choice of the 200 mg Q3W as an appropriate dose for the switch to fixed dosing is based on simulations performed using the population PK model of pembrolizumab showing that the fixed dose of 200 mg every 3 weeks will provide exposures that 1) are optimally consistent with those obtained with the 2 mg/kg dose every 3 weeks, 2) will maintain individual patient exposures in the exposure range established in melanoma as associated with maximal efficacy response and 3) will maintain individual patients exposure in the exposure range established in melanoma that are well tolerated and safe.

A fixed dose regimen will simplify the dosing regimen to be more convenient for physicians and to reduce potential for dosing errors. A fixed dosing scheme will also reduce complexity in the logistical chain at treatment facilities and reduce wastage.

4.2.3 Rationale for Endpoints

Cisplatin and pembrolizumab appear to be well tolerated as single agents and have FDA approved doses and indications. These two drugs have non-overlapping mechanisms of action. Cisplatin in combination with radiation is well tolerated and considered standard treatment in laryngeal carcinoma patients who are treated with an organ preservation approach. There has been no reported clinical experience with the combination of cisplatin-radiation and pembrolizumab in locally advanced laryngeal carcinoma patients. Therefore a phase I/II design, wherein a limited phase I run in cohort is initially enrolled, was felt to be most appropriate to study this combination, with laryngectomy-free survival as a composite endpoint to reflect both oncologic and functional outcome as the primary endpoint of interest.

4.2.3.1 Efficacy Endpoints

There is intriguing preclinical and clinical data suggesting that combination of radiation and PD-1 inhibitor can augment the immunologic anti-tumor response to radiation. The

study explores whether chemoradiation combined with a PD-1 inhibitor have synergistic effects, resulting fewer salvage laryngectomies for persistent/ recurrent disease or dysfunctional larynx, and allow for improved quality of life in laryngeal cancer survivors.

Specifically, this study hypothesizes that organ preservation will improve as a consequence of this synergistic effect.

Therefore in addition to above, exploring objective response rates to the combination of pembrolizumab with chemoradiation will be secondary endpoints. Overall survival and progression free survival will be examined as well. If encouraging response rates, and overall and progression free survival are observed in this cohort of patients, further study of the combination in this disease will be justified.

4.2.3.2 Biomarker Research

1. Archived tumor tissue at diagnosis, during treatment tumor biopsies, salvage laryngectomy tissues, and potential biopsies from regional and systemic recurrent disease will be used to examine tumor PD-L1 expression, Tumor infiltrating immune cell phenotypes, global gene expression by RNAseq, and whole genome sequencing in an attempt to define a gene set critical for clinical response to pembrolizumab and chemoradiation and correlate these with clinical benefit and emergence of resistance from combination of Pembrolizumab and chemoradiation.
2. Examine peripheral blood mononuclear cell phenotypes in pre-treatment, during treatment, and post-treatment in blood samples using flow cytometric evaluation of CD3, CD4, CD8, CD14, PD-1, PD-L1, PD-L2, and correlate these with clinical benefit from combination of Pembrolizumab and chemoradiation. In addition to these specific protein biomarkers, both tissue and blood derivatives can be subjected to proteomic profiling studies using a variety of platforms that could include but are not limited to immunoassay, liquid chromatography/mass spectrometry. This approach could identify novel protein biomarkers that could aid in patient selection for pembrolizumab and chemoradiation. Combination therapy.
3. Examine circulating tumor DNA in pre-treatment, during treatment, and post-treatment blood samples, and correlate circulating tumor DNA levels as a potential biomarker for clinical benefit or emergence of early resistance from combination of Pembrolizumab and chemoradiation.
4. Circulating tumor cells (CTCs) hold great promise as a readily available source material that can offer real-time insight into a tumor's genomic architecture. CTCs can be detected in head and neck cancer patients and appear to have prognostic importance. We propose to collect CTCs and assess PD-L1 expression in CTCs and attempt to correlate PD-L1 expression in CTCs with patient's primary tumor and with efficacy parameters.
5. Examine rates of speech and swallowing dysfunction after completion of treatment with combination of Pembrolizumab and chemoradiation.
6. Examine correlation of post treatment PET scan findings with clinical benefit in Pembrolizumab treated patients.

5.0 METHODOLOGY

5.1 Entry Criteria

5.1.1 Diagnosis/Condition for Entry into the Trial

Patients with biopsy-proven laryngeal squamous cell carcinoma that are candidates for curative treatment with chemoradiation.

5.1.2 Subject Inclusion Criteria

In order to be eligible for participation in this trial, the subject must:

1. Biopsy-proven, previously untreated stage III or IV squamous cell carcinoma of the larynx, Primary tumor stage (T2, T3) and nodal stage (N0,N1,N2,N3).
2. Be willing and able to provide written informed consent/assent for the trial.
3. Be ≥ 18 years of age on day of signing informed consent.
4. Have measurable disease based on RECIST 1.1.
5. Be willing to provide tissue from a newly obtained core or excisional biopsy of a tumor lesion. *Newly-obtained is defined as a specimen obtained up to 6 weeks (42 days) prior to initiation of treatment on Day 1. Subjects for whom newly-obtained samples cannot be provided (e.g. inaccessible or subject safety concern) may submit an archived specimen only upon agreement from the Sponsor.*
6. Have a performance status of 0 or 1 on the ECOG Performance Scale.
7. Anticipated survival minimum 12 months.
8. Patient is > 5 years free of another primary malignancy, except: a) if the other malignancy is basal cell carcinoma or cervical carcinoma in situ or b) if the other primary malignancy is not considered clinically significant and is requiring any active intervention
9. Demonstrate adequate organ function as defined in Table 1, all screening labs should be performed within 10 days of treatment initiation.

Table 1 Adequate Organ Function Laboratory Values

System	Laboratory Value
Hematological	
Absolute neutrophil count (ANC)	$\geq 1,500$ /mcL
Platelets	$\geq 100,000$ / mcL
Hemoglobin	≥ 9 g/dL or ≥ 5.6 mmol/L without transfusion or EPO dependency (within 7 days of assessment)
Renal	
Serum creatinine OR Measured or calculated ^a creatinine clearance (GFR can also be used in place of creatinine or CrCl)	≤ 1.5 X upper limit of normal (ULN) OR ≥ 60 mL/min for subject with creatinine levels > 1.5 X institutional ULN
Hepatic	
Serum total bilirubin	≤ 1.5 X ULN OR

	Direct bilirubin \leq ULN for subjects with total bilirubin levels $>$ 1.5 ULN
AST (SGOT) and ALT (SGPT)	\leq 2.5 X ULN OR \leq 5 X ULN for subjects with liver metastases
Albumin	\geq 2.5 mg/dL
Coagulation	
International Normalized Ratio (INR) or Prothrombin Time (PT)	\leq 1.5 X ULN unless subject is receiving anticoagulant therapy as long as PT or PTT is within therapeutic range of intended use of anticoagulants
Activated Partial Thromboplastin Time (aPTT)	\leq 1.5 X ULN unless subject is receiving anticoagulant therapy as long as PT or PTT is within therapeutic range of intended use of anticoagulants
^a Creatinine clearance should be calculated per institutional standard.	

10. Female subject of childbearing potential should have a negative urine or serum pregnancy within 72 hours prior to receiving the first dose of study medication. If the urine test is positive or cannot be confirmed as negative, a serum pregnancy test will be required.
11. Female subjects of childbearing potential should be willing to use 2 methods of birth control or be surgically sterile, or abstain from heterosexual activity for the course of the study through 120 days after the last dose of study medication (Reference Section 5.7.2). Subjects of childbearing potential are those who have not been surgically sterilized or have not been free from menses for $>$ 1 year.
12. Male subjects should agree to use an adequate method of contraception starting with the first dose of study therapy through 120 days after the last dose of study therapy.

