5.1.3 Subject Exclusion Criteria

The subject must be excluded from participating in the trial if the subject:

1. Patients with T1 primary tumor or T4 large volume tumor that has resulted in larynx dysfunction at baseline (for example tumor largely penetrating into base of tongue and resulting in inability to swallow at baseline)
2. Prior radiation therapy to larynx area or involved neck.
3. Distant metastasis. Small lesions (for example, small nodule in lung) that are not clinically or radiographically suggestive of metastasis do not require biopsy for confirmation.
4. Prior complications from former therapies, such as history of radiation pneumonitis that, in the opinion of the investigator, may have risk of increasing toxicity with anti-PD1 therapy.
5. Is currently participating and receiving study therapy or has participated in a study of an investigational agent and received study therapy or used an investigational device within 4 weeks of the first dose of treatment.

6. Has a diagnosis of immunodeficiency or is receiving systemic steroid therapy or any other form of immunosuppressive therapy within 7 days prior to the first dose of trial treatment.
7. Has a known history of active TB (Bacillus Tuberculosis)
8. Hypersensitivity to pembrolizumab or any of its excipients.
9. Patients who have not recovered (i.e., \leq Grade 1 or at baseline) from adverse events due to a previously administered agent.
 - Note: Subjects with \leq Grade 2 neuropathy are an exception to this criterion and may qualify for the study.
 - Note: If subject received major surgery, they must have recovered adequately from the toxicity and/or complications from the intervention prior to starting therapy.
10. Has a known additional malignancy that is progressing or requires active treatment. Exceptions include basal cell carcinoma of the skin or squamous cell carcinoma of the skin that has undergone potentially curative therapy or in situ cervical cancer.

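### Two binding eligibility rules do not work as printed: inclusion 8(b) admits essentially no one once exclusion 10 is applied, and the albumin floor of 2.5 mg/dL excludes no one

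*Combined protocol and SAP*

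**What the plan says.** **Second malignancies.** Inclusion 8 in section 5.1.2 sets the base rule: "Patient is > 5 years free of another primary malignancy, except". Two exceptions follow. Exception (a) applies "if the other malignancy is basal cell carcinoma or cervical carcinoma in situ". Exception (b) applies "if the other primary malignancy is not considered clinically significant and is requiring any active intervention".

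Exclusion 10 in section 5.1.3 removes a patient who "Has a known additional malignancy that is progressing or requires active treatment". It has its own carve-outs: "Exceptions include basal cell carcinoma of the skin or squamous cell carcinoma of the skin that has undergone potentially curative therapy", and also in situ cervical cancer.

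**Albumin.** Inclusion 9 makes the laboratory limits binding: "Demonstrate adequate organ function as defined in Table 1". The albumin row of Table 1 sets a floor of 2.5 mg/dL. The haemoglobin row of the same table sets its floor of 9 in g/dL. Albumin is on the chemistry list in Table 5, so a screening value will exist for each patient.

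**The concern.** Exception 8(b) joins two conditions: the second cancer is not significant, and it does need intervention. The verb *is* appears again before *requiring*, so the earlier *not* does not grammatically reach the second condition. Yet *any* sits naturally only in a negated clause, which suggests that a *not* was dropped. As printed, the exception points at patients whom exclusion 10 then removes, and it leaves out the patients it was evidently meant to help.

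The albumin floor looks wrong because of its unit. A limit printed in mg/dL is 1,000 times lower than the same number in g/dL.

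Both are entry rules that sites apply patient by patient. At stake is a wrong screening result for a site that follows the text: a rejection that was not intended under 8(b), and a laboratory check that never takes effect.

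**Working it through.** **Inputs.** Inclusion 8, with exceptions (a) and (b), and inclusion 9 with Table 1, from section 5.1.2; exclusion 10 from section 5.1.3. One assumption from outside the documents: patient serum albumin lies between 0.5 and 5 g/dL, a deliberately wide range.

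**Step 1: 8(b) against exclusion 10.** Take a second primary within 5 years that is not covered by 8(a) or by an exclusion 10 carve-out. Treat the intervention in 8(b) and the treatment in exclusion 10 as the same thing; the objection below relaxes this. A patient is eligible only if 8(b) is met and exclusion 10 is not triggered.

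| Clinically significant? | Intervention needed? | 8(b) as printed | Exclusion 10 (treatment limb) | Eligible as printed | Eligible if 8(b) read *not requiring* |
|---|---|---|---|---|---|
| No | No | not met | not triggered | No | Yes |
| No | Yes | met | triggered | No | No |
| Yes | No | not met | not triggered | No | No |
| Yes | Yes | not met | triggered | No | No |

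As printed, 0 of 4 combinations are eligible. With the second condition negated, 1 of 4 is: insignificant and needing no intervention. That reading agrees with exclusion 10.

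The first row fails on inclusion 8 alone. Exclusion 10 plays no part in it and cannot repair it, since a patient must meet every inclusion criterion.

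**Step 2: the skin-cancer corner.** Squamous cell skin cancer after potentially curative therapy is exempt from exclusion 10 but is not listed in 8(a). Within 5 years, such a patient can enter only through 8(b). As printed, that requires the cancer to be insignificant and still to need some intervention. This is the one route by which 8(b) can admit someone. The same patient needing nothing further fails inclusion 8, although exclusion 10 spares them.

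**Step 3: the albumin floor.** With 1 g/dL = 1,000 mg/dL:

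- Floor as printed: 2.5 / 1,000 = 0.0025 g/dL.
- Low end of the assumed range: 0.5 × 1,000 = 500 mg/dL, and 500 / 2.5 = 200 times the floor.
- High end: 5 × 1,000 = 5,000 mg/dL, and 5,000 / 2.5 = 2,000 times the floor.

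No patient in the range falls below the floor. For comparison, the same number in g/dL would be 2.5 × 1,000 = 2,500 mg/dL, which lies inside the range of 500 to 5,000 and could therefore exclude patients.

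No sample-size or power figure enters either check.

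**The case against.** The strongest reply is that these are drafting slips with a recoverable meaning. An experienced screener would read 8(b) as excusing an insignificant cancer that needs nothing done, and exclusion 10 already keeps out cancers under treatment, so 8(b) should lead to no unsafe enrolment. That is fair on safety. It does not help the patient in the first row of the table, who fails the written criterion whatever the screener believes was intended.

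Intervention in 8(b) could also be read more broadly than treatment in exclusion 10, so that a few patients needing some non-treatment intervention would pass. The documents define neither term. This, with the skin-cancer corner, is why the conclusion is *essentially* no one and not a strict zero.

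For albumin, exclusion 15 lets the treating investigator exclude a patient for a laboratory abnormality, and the other Table 1 limits, performance status and anticipated survival still apply. So it would be too strong to say that patients have no protection. What is missing is a working albumin threshold: exclusion 15 is a judgement, not a limit.

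A reader might infer four further things that the documents do not support:

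- *Every such screening decision is a deviation.* It is not. A site that applies the printed text complies with it; the trouble is that text and evident intent diverge.
- *Many patients are wrongly rejected because the disease is linked to smoking.* Section 4.2.1 mentions smoking to justify immune therapy. It says nothing about second primaries or how often they are insignificant.
- *The two skin-cancer lists are a separate contradiction.* Inclusion and exclusion criteria are cumulative, so the stricter one governs. Once 8(b) is corrected, a treated squamous cell skin cancer judged insignificant and needing nothing further passes through it, and most of the mismatch disappears.
- *The design is weakened.* The 47 patients, the one-sided 10% level and the 80% power in section 8.1 depend on neither criterion.

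**Conclusion.** The point holds for both criteria as printed. Inclusion 8(b), read with exclusion 10, admits essentially no one and shuts out an insignificant second primary that needs no intervention, unless 8(a) covers it. The albumin floor excludes no one across the assumed range, with a margin of at least 200-fold, so that conclusion does not depend on the exact range chosen.

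The 8(b) result rests on the literal grammar and on treating active intervention and active treatment as equivalent. The rejection of the patient needing no intervention rests on the grammar alone. The albumin row reads as intact, although an error in reading the unit from the PDF cannot be wholly excluded.

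The number of patients affected cannot be estimated, because the documents give neither a rate of second primaries nor an albumin distribution. This is a correction to binding entry rules that should be made; it is not a challenge to the design or analysis.

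**What to change.** 1. Reconcile inclusion 8(b) with exclusion 10. The wording suggests a missing *not* before *requiring*; the study team should confirm the intended meaning and use one term for intervention or treatment in both places.
2. In the same edit, check that squamous cell skin cancer after potentially curative therapy is handled the same way under inclusion 8 and exclusion 10.
3. Correct the albumin unit in Table 1. Haemoglobin in the same table is in g/dL; the study team must confirm both the intended value and the unit.

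The cost is a few words in one amendment, with the IRB approval that section 10.5 requires before any change takes effect. The sample size and the analysis stay as they are.
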